Rheumatoid arthritis, inflammatory bowel disease, psoriasis +/- arthritis, ankylosing spondylitis and systemic lupus erythematosus affect 1 in 30 adults in the UK, and are treated with immune suppressing drugs such as methotrexate, azathioprine and sulfasalazine etc. [4-9]. These medicines can cause symptomatic side-effects such as nausea, vomiting, headache, infections etc., and asymptomatic side-effects such as acute liver or kidney injury, or low blood cell count. Clinical experience and research studies identified in our scoping review suggest that both symptomatic and asymptomatic side-effects generally occur within the first six months of starting treatment [10-14], and, because of this increased risk of drug toxicity, treatment is initiated in a hospital clinic with dose escalation guided by disease activity, and fortnightly-to-monthly tests of full blood count, renal and liver function performed to detect any asymptomatic abnormalities early. Unless there are early side-effects and the treatment is stopped, most patients achieve their target dose between three to four months of starting treatment. Just after this, the responsibility for prescribing and monitoring, including with three-monthly blood tests is handed-over to the patients' general practitioner (GP). The intended purpose of such monitoring is to facilitate early detection of an abnormality, allowing the offending treatment to be stopped before any permanent damage occurs. However, there is scant evidence that long-term use of these immune suppressing medicines causes blood, liver, or kidney damage [10-14]. Thus, this strategy for long-term monitoring with periodic blood tests for all patients appears to be based on convention, inertia, and perceived safety, rather than on a robust evidence base.

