Cohort entry and start of follow-up: At first prescription and day 180 of the first primarycare prescription of a drug of interest respectively. Separate cohorts will be built for each drug.

Cohort exit: Earliest of target-organ adverse event, drug discontinuation, death, moving to a different practice, 5-year follow-up time, or 31/12/2019 (study end date).

Inclusion criteria:

[1] Diagnosis of any common inflammatory disease i.e. RA, inflammatory bowel disease, psoriasis +/- arthritis, ankylosing spondylitis, systemic lupus erythematosus, or reactive arthritis. These are the commonest inflammatory conditions treated with immune-suppressive drugs.

[2] Age ≥18 years at diagnosis.

[3] At least one GP prescription of methotrexate, azathioprine (or mercaptopurine), aminosalicylates, sulfasalazine, mycophenolate. These are the most commonly prescribed immune-suppressing drugs for which blood test monitoring is recommended.
[4] Meeting CPRD data quality standards (UTS for Gold and acceptable flag for Aurum) and with a continuous registration for at least one year before the first date of diagnosis of inflammatory disease in CPRD Gold and CPRD Aurum.

The requirement to have one-year disease free registration in the CPRD prior to first date of inflammatory disease diagnosis is to allow for the identification of incident cases, and those newly commenced on immune-suppressing drugs. This will exclude prevalent cases of inflammatory diseases on long-term hospital prescribed immune-suppressive drugs who have recently switched to GP prescription due to implementation of primary-care/secondary-care shared care prescribing in their area.

Exclusion criteria: Presence of any of the below prior to cohort entry:

[1] eGFR < 15 ml/min or chronic kidney disease stage 4 or 5.

[2] Chronic liver disease: Autoimmune hepatitis, hepatitis B or C, cirrhosis

[3] Pre-existing hematological abnormalities: Myelodysplasia, primary hematological diseases causing neutropenia or thrombocytopenia.

[4] Prescription of the immunosuppressive drugs listed above before first inflammatory disease diagnosis date.

[5] Registered in GP practices not meeting CPRD data quality standard at cohort entry.

Selection of comparison group(s) or controls

A comparison group is not applicable in the context of risk prediction modelling. Exposures, outcomes and covariates

Predictors of drug discontinuation: Candidate prognostic factors will be identified using two approaches:

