[1] Theory driven based on prior knowledge: A list of recognised prognostic factors for abnormal monitoring blood test results have been developed based on the research teams' clinical experience. The a priori agreed prognostic factors include: age, sex, body mass index, alcohol consumption, smoking, CKD stage 3, type 2 diabetes, and prescription of selected drugs that increase risk of acute kidney injury or transaminase elevation at baseline.

[2] Evidence based, based on systematic review: A systematic review of existing literature is currently underway to identify other prognostic factors. This will provide additional candidate predictors (PROSPERO: CRD42020208049).

The presence of comorbid and lifestyle prognostic factors will be ascertained using primarycare diagnoses and lifestyle data collected in the two-years preceding cohort entry. The presence of prescription prognostic factors will be ascertained using primary-care prescriptions in the 180 days preceding cohort entry.

Outcomes

Primary outcome: Target organ specific adverse event resulting in drug discontinuation from 6 months of initial primary-care prescription to until 5-years after the initial prescription.

This will be defined as drug discontinuation with either (a) diagnosed with target organ damage based on clinical code, or (b) significant abnormal blood test results.

Drug discontinuation due to abnormal monitoring blood test results will be defined as present when there is:

(a) a gap between two prescriptions, or between last prescription date and earliest of death date, moving to a different practice, 5-year follow-up time, or 31/12/2019 (study end date) of \geq 90 days, and

(b) an abnormal blood-test result in the 15 days preceding or 45 days after the last prescription date. The 15-day preceding window is to allow for any delay in acting on abnormal blood-test results.

Abnormal blood test results will be defined according to the British Society for Rheumatology DMARD monitoring guidelines 1, and CKD progression will be defined as per the Kidney Disease Improving Global Outcomes guideline 20122:

- White blood cells <3.5x109/L,
- Neutrophils <1.6x109/L,
- Platelets <140x109/L,
- Alanine Transaminase and/or Aspartate Transaminase >100 units/L,

• CKD progression defined as creatinine difference > 26 micro mol/L above the first or second preceding result or chronic kidney disease stage progression.

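### The primary outcome does not ask whether a blood-count or liver abnormality is new, and no listed predictor records that it was already present at day 180

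*Protocol*

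**What the plan says.** The Protocol sets out the primary outcome twice, under Outcomes to be measured and again under Exposures, outcomes and covariates. The blood-test route needs a prescribing gap of at least 90 days together with "an abnormal blood-test result in the 15 days preceding or 45 days after the last prescription date".

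Four of the listed abnormalities are absolute: "White blood cells <3.5x109/L", "Neutrophils <1.6x109/L", "Platelets <140x109/L" and "Alanine Transaminase and/or Aspartate Transaminase >100 units/L". The renal item is different in kind. It is a "creatinine difference > 26 micro mol/L above the first or second preceding result", or progression of CKD stage.

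Steps 1–4 of Primary outcome identification take everyone with a qualifying gap, extract results and codes from the 60-day window, and count those with an abnormal result or code. Nothing in these steps looks at earlier values or at the reason for stopping.

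Follow-up starts at day 180 of the first primary-care prescription, but the exclusions apply before cohort entry, which is the first prescription itself. The haematological exclusion reads "Myelodysplasia, primary hematological diseases causing neutropenia or thrombocytopenia". The liver exclusion is likewise a list of diagnoses. The agreed predictors are demographic, lifestyle, comorbidity and co-prescription items. None is a blood count or a transaminase.

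**The concern.** The model is meant to predict target-organ damage arising after six months of treatment. A fixed cut-off without a look-back cannot separate a fall in white cells at month 20 from a white cell count that has stayed at, say, 3.2 since before the drug was started. The second patient may take the drug for years and then stop because of remission, preference or a return to hospital prescribing, which the CPRD does not record. If a routine test falls in the window, that stop enters the data as drug toxicity.

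Two features make this more than coding noise. An abnormality that appears between first prescription and day 180 and then persists escapes the exclusions altogether. And with no predictor describing blood results at day 180, the model has to spread these events over age, sex, comorbidity and co-prescription. Event counts, coefficients, calibration and the decision-curve thresholds are all affected. External validation in the other CPRD database uses the same outcome definition, so it would not show the problem.

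**Working it through.** **The plan's own figures.** Under Feasibility counts there were 1,262 events among 15,670 methotrexate users: 1,262/15,670 = 8.05%, which agrees with the stated 8%. The 99% half-width is 2.576 × √(0.08 × 0.92/15,670) = 0.56%, against a stated 0.55%. The model sample size also reproduces. With 50 parameters, model R² 0.027 and a shrinkage target of 0.9 (my assumption; the Protocol does not state it), n = 50/[(0.9 − 1) × ln(1 − 0.027/0.9)] = 16,415, against 16,416. None of these is in dispute.

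**Chance that an unrelated stop has a test in the window.** The window is 15 + 45 = 60 days. Study background A describes primary-care follow-up as "including with three-monthly blood tests is handed-over" to the GP, so an interval of about 91 days. If testing is regular and unrelated to the stop, w = 60/91 = 0.66. It would be 1 with monthly tests. It would be lower if testing ended with the last prescription; at that extreme only the 15 preceding days count, and 15/91 = 0.16.

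**Assumptions not in the documents.** Share of entrants with a stable out-of-range count or ALT/AST, q = 1–3%. Share of them stopping for an unrelated reason, D = 30–50%.

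**False events as a share of the cohort**, f = q × D × w:
- Low: 0.01 × 0.30 × 0.66 = 0.20%
- High: 0.03 × 0.50 × 0.66 = 0.99%

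**As a share of counted events.** The denominator depends on what the risk figure contains.
- The 8.05% is a counted figure, so false events are already inside it: 0.20/8.05 = 2.5% and 0.99/8.05 = 12%. In a cohort of 15,670 that is about 31 to 155 of 1,262 events.
- If instead the true risk were 2%, false events come on top: 0.20/(2 + 0.20) = 9% and 0.99/(2 + 0.99) = 33%.

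**Wider inputs.** With q = 0.5–3%, D = 30–50% and w = 0.66–1, the methotrexate cohort would hold about 15 to 235 such events, or 1.2% to 18.6% of 1,262.

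**The case against.** The best defence concerns size. Limitation [3] says that people with chronic liver disease or cytopenia may be prescribed for by hospital specialists and so be absent from the CPRD, and that giving these drugs to people with such serious illnesses is very rare. Monitoring also exists so that treatment can be stopped when a result is abnormal, which makes an ALT persistently above 100 in someone still treated at day 180 less likely than a mildly low white count. Both points argue for the lower end of the assumed prevalence. Neither reaches a stable, mild abnormality without a diagnosis.

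The sponsor can also point to the 505 sampled methotrexate cases, 95% of which had no alternative explanation recorded in the CPRD. This is the only empirical evidence in the Protocol and it deserves weight, since an abnormality caused by the underlying disease could fall within its scope. But it comes from methotrexate users in the earlier rheumatic-disease study, it did not ask whether the value predated day 180, and no such review is described here for the other drugs.

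Limitation [1] prefers over-counting on safety grounds. That argument is about the outcome rate when biologic prescribing is unrecorded. It does not deal with coefficients or calibration.

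A reader might go further and infer that the primary outcome must be redefined to require a new abnormality. The documents do not support that. Such a rule would drop genuine worsening in patients who were already abnormal, and it would not match the creatinine criterion, which counts any sufficient rise whatever the starting level.

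**Conclusion.** The gap is real on the text: abnormalities already present at day 180 can be counted as later drug toxicity, and the agreed predictors give the model no means of identifying those patients unless the systematic review happens to add one. The size is unknown. The 2.5–12% and 9–33% ranges rest on assumed prevalence and assumed unrelated stopping, and on regular three-monthly testing.

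Two stronger readings should be resisted. First, such a patient does not become an event on every unrelated stop; an out-of-range result or code in the 60-day window is still needed. Second, dividing 0.20% and 0.99% by 2% gives 10% and about 50%, and a reader might take half the events to be false. That quotient is a ratio of false to true events. As a share of counted events the ceiling is 33%. The 2% itself is only an illustration of low risk: in the Protocol's literature summary, below 2% is a clinical-trial figure for methotrexate after the first year, whereas the planning rate of 0.02 per person-year over about 4.5 years gives 0.02 × 4.5 = 9%.

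This is a worthwhile, inexpensive improvement to the plan and does not invalidate the outcome.

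**What to change.** Keep the primary definition and make two additions.

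1. Add a candidate predictor, measured at day 180: any white cell, neutrophil, platelet or ALT/AST result beyond its threshold between first prescription and day 180. This fits objective [1], which refers to factors available at six months, but the stated look-back windows end at cohort entry, so the text must say that this item is taken later. State also how patients with no test in that period are handled.
2. Pre-specify a sensitivity analysis in which a count or ALT/AST abnormality is an event only if the last result before day 180, or the preceding result in follow-up, was within threshold. For each drug, report the number of events reclassified and the change in calibration.

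The cost is one or a few more parameters within the 50 allowed for, and extraction of earlier results. Step 2 covers only the 60-day window, but the creatinine rule already requires preceding tests and the first-year testing rule under missing data already requires a count of them. The sensitivity analysis will have fewer events and will omit further worsening in patients who were already abnormal, which is the reason to leave the primary definition as it is.

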(a) a gap between two prescriptions, or between the last prescription date and earliest of death date, moving to a different practice, 5-year follow-up time, or 31/12/2019 (study end date) of \geq 90 days, and

(b) the last prescription is preceded in up to 15 days by abnormal blood test results (to account for any delay in acting on abnormal results) or followed by an abnormal test result in the next 45 days.

Abnormal blood test results will be defined according to the British Society for Rheumatology DMARD monitoring guidelines1, and CKD progression will be defined as per the Kidney Disease Improving Global Outcomes guideline 20122:

- White blood cells <3.5x109/L,
- Neutrophils <1.6x109/L,
- Platelets <140x109/L,
- Alanine Transaminase and/or Aspartate Transaminase >100 units/L,

• CKD progression defined as creatinine difference > 26 micro mol/L above the first or second preceding blood-test result or chronic kidney disease stage progression.

In addition to the above blood-test abnormalities, in people with psoriasis, methotrexate discontinuation will be defined to be due to blood-test abnormalities if (i) serum amino-terminal pro-peptide of type III procollagen (PIIINP) is > 8 mg/L on two previous occasions; (ii) if three previous PIIINP measurements were >4.2 mg/L in the previous 12-month period; or (iii) if previous PIIINP measurement was > 10 mg/L as per guidelines for the British Association of Dermatologists [3].

Secondary outcome: Drug discontinuation due to any reason.

Defined as present if there is a gap between two prescriptions, or between last prescription date and earliest of death date, moving to a different practice, 5-year follow-up time, or 31/12/2019 (study end date) of ≥ 90 days.

Objectives, specific aims and rationale

The overall purpose of this study is to ascertain the optimum strategy of blood testing for adults with common inflammatory conditions treated with immune-suppressing drugs after the first six months of primary-care prescription. By strategy we mean the optimum frequency of testing, and how the frequency of testing should alter according to the individual's risk.

The objectives are to:

[1] Develop and validate a prediction model estimating an individual's risk of target-organ damage conditional on their values of multiple prognostic factors available at six months of immune-suppressing drug prescription.

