[2] Identify incidence of drug discontinuation due to any reason and due to abnormal monitoring blood test results in each year of prescription.

Synergy with ongoing research: We have an ISAC approved study (reference number 19_275R) developing a risk-prediction score for liver, blood or kidney damage from methotrexate and leflunomide in people with auto-immune rheumatic diseases, using data from the Clinical Practice Research Datalink (CPRD).

We are seeking approval for additional work to [1] conduct prediction modelling for azathioprine, sulfasalazine, aminosalicylates (such as mesalazine), and mycophenolate, and [2] expand analysis of methotrexate to include patients with psoriasis (without psoriatic arthritis) and inflammatory bowel disease.

Leflunomide is only licenced for the treatment of RA and psoriatic arthritis and we do not propose to expand the modelling to other common inflammatory conditions for this drug for this reasons.

We can confirm that these analyses were not included in our previously approved application.

Study background

A. What is the problem being addressed?

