In addition, in people with psoriasis (but without arthritis), methotrexate discontinuation will be defined to be due to blood-test abnormalities if (i) serum amino-terminal propeptide of type III procollagen (PIIINP) is > 8 mg/L on two previous occasions; (ii) if three previous PIIINP measurements were >4.2 mg/L in the previous 12-month period; or (iii) if previous PIIINP measurement was > 10 mg/L as per guidelines for the the British Association of Dermatologists [3].

Primary outcome identification: Study participants who have the outcome of interest will be identified as follows:

Step 1: All participants with drug discontinuation as defined above will be identified.

Step 2: The results of their blood tests from up to 15 days before and 45 days after the last DMARD prescription date, and the dates of blood tests will be extracted.

Step 3: All other Read code entries in the clinical and investigation files indicating abnormal blood test results within this 60-day period (-15 to + 45 days), and the date of such entry will be extracted.

Step 4: Participants with abnormal blood test results or a Read code specifying abnormal blood test results within this period and their date of event will be ascertained.

Secondary outcome: Drug discontinuation due to any reason. Defined as a gap between two prescriptions, or between last prescription date and earliest of death date, moving to a different practice, 5-year follow-up time, or 31/12/2019 (study end date) of \geq 90 days. Data/statistical analysis

Mean (standard deviation), and n (%) will be used for descriptive purposes.

Derivation and validation of the risk prediction model:

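### The PIIINP part of the methotrexate primary outcome is given two different populations, and the stated 60-day identification window does not fit its look-back criteria

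*Protocol*

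**What the plan says.** **Population.** In the Protocol section Outcomes to be measured, the rule reads "In addition to the above blood-test abnormalities, in people with psoriasis, methotrexate discontinuation will be defined to be due to blood-test abnormalities if" one of three PIIINP conditions holds. In the later Outcomes section (under Exposures, outcomes and covariates) the same three conditions apply "in people with psoriasis (but without arthritis), methotrexate discontinuation will be defined to be due to blood-test abnormalities if" they are met. The Inclusion criteria admit "psoriasis +/- arthritis, ankylosing spondylitis, systemic lupus erythematosus, or reactive arthritis", along with rheumatoid arthritis and inflammatory bowel disease. Under Synergy with ongoing research, the application seeks to "expand analysis of methotrexate to include patients with psoriasis (without psoriatic arthritis) and inflammatory bowel disease".

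**Criteria.** Both statements list the same three conditions:
- (i) PIIINP "is > 8 mg/L on two previous occasions", with no time limit;
- (ii) "if three previous PIIINP measurements were >4.2 mg/L in the previous 12-month period";
- (iii) a single previous value above 10 mg/L, with no time limit.

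**Identification.** Under Primary outcome identification, Step 1 finds everyone who discontinued. Step 2 extracts "The results of their blood tests from up to 15 days before and 45 days after the last DMARD prescription date". Step 3 adds Read codes from the same 60 days. Step 4 counts as events those with an abnormality inside that period and records the event date. No step mentions PIIINP or an earlier test history.

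**The concern.** Two things look wrong.

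First, the two definitions disagree about methotrexate users who have psoriasis with arthritis. If such a patient stops the drug and only PIIINP qualifies, the patient has a primary event under one text and a stop for another reason under the other. Neither text is marked as replacing the other.

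Second, the identification steps are a stated algorithm, and taken literally they do not collect the data that two of the three PIIINP criteria need. A programmer who follows the steps largely disables (i) and (ii). One who treats PIIINP as a separate route has no limit on how old the two results under (i) may be, and no rule for dating the event in a time-to-event model.

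At stake is the outcome status of methotrexate users with psoriasis whose event depends on PIIINP alone. Psoriasis without psoriatic arthritis is one of the two groups this application adds to the methotrexate model.

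**Working it through.** **1. The two populations side by side**

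| Methotrexate user who stops, with only PIIINP qualifying | Outcomes to be measured | Outcomes (detailed section) |
|---|---|---|
| Psoriasis without arthritis | event | event |
| Psoriasis with arthritis | event | not an event |

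The second row is not empty by design, because the Inclusion criteria admit psoriasis with arthritis.

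**2. The window**

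The protocol's own figure reproduces: 15 + 45 = 60 days.

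**3. How many results can fall in it**

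Inputs: a window of 60 days (Steps 2-3), and a regular spacing of d days between PIIINP tests. The protocol gives no PIIINP interval, so d is an assumption. The three-monthly interval that the Study background gives for general blood monitoring is used as one value (91 days).

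Formulas: the largest number of results in a closed 60-day window is floor(60/d) + 1. Three results span 2d days.

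| d (days) | Most results in 60 days | Span of three results (days) |
|---|---|---|
| 28 | 3 | 56 |
| 30 | 3 | 60 |
| 31 | 2 | 62 |
| 60 | 2 | 120 |
| 61 | 1 | 122 |
| 91 | 1 | 182 |

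- Criterion (ii), three results: possible inside the window only at a spacing of 30 days or less.
- Criterion (i), two results: possible only at 60 days or less.
- Criterion (iii), one result: can be met inside the window.

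**4. Share of the 12-month look-back that is extracted**

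Counted back from the last prescription, the window holds 15 of 365 days: 15/365 = 4.1%. Counted back from the end of the window, which is the most generous anchor, it holds 60/365 = 16.4%. Either way, most of the period named in (ii) is not extracted.

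**5. The other reading**

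Suppose PIIINP is a route outside the window.
- Criterion (ii) then has its own 12-month limit.
- Criterion (i) has none. Two high values from any earlier time would qualify a later stop, although the general rule ties a stop to an abnormal result within -15 to +45 days.
- Step 4 records an event date, but for an event built from several earlier results the text does not say which date that is. Follow-up starts at day 180 of prescription, so if the date of an old result were used, it could fall before follow-up begins.

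**6. What cannot be calculated**

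The number of affected events needs the PIIINP testing frequency, the number of PIIINP-only events, and the number of methotrexate users with psoriatic arthritis. The protocol gives none of these.

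**The case against.** The strongest reply has four parts.

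*The population difference is a slip.* The description of the methotrexate expansion names psoriasis without psoriatic arthritis, which matches the detailed Outcomes section and suggests that the earlier section dropped a qualifier. That is plausible. But the expansion text does not mention PIIINP and the cohort includes psoriasis with arthritis, so it does not settle the matter.

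*Steps 2-4 are shorthand.* The creatinine rule also needs the first or second preceding result, which at three-monthly testing would usually lie outside the window, so the steps cannot list every result used. The PIIINP rule is also introduced as an addition. This stands as a possible reading. It does not remove the problem: the creatinine rule compares a current result with earlier ones, while the PIIINP rule names only previous values and no current one.

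*Extraction detail belongs in an analysis plan, which is not at hand.* A mere omission would be no finding. Here the protocol states a window that, as written, defeats an outcome it also states.

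*Stronger conclusions go too far.* This stands, on three counts:
- A reader might infer that any stop after an old high value counts under (iii). That criterion is worded in the singular and more naturally means the latest result.
- A reader might assume that 5-10% of psoriasis users ever meet (i) or (iii) and that 40-60% stop within 5 years, giving 0.05 × 0.40 = 2 to 0.10 × 0.60 = 6 percentage points of extra events. Neither input is in the documents. The product also treats raised PIIINP and stopping as independent, and assumes that no such stop already qualifies through another test.
- A reader might expect a calibration difference between Gold and Aurum. The protocol plans the same code search strategy for both, and one reading applied to both would not by itself create a difference.

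**Conclusion.** The point holds in a limited form. The protocol contradicts itself on who is subject to the PIIINP criteria. Its identification steps, read literally, cannot establish criterion (ii) unless three results fall within 60 days, and would rarely establish (i). The alternative reading leaves (i) without a time limit or an event date.

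The consequence is a risk of misclassification, confined to methotrexate users with psoriasis whose event rests on PIIINP alone. A reader might go further and say that events are misclassified. The documents do not show that, and give no basis for a number. The statement about (i) and (ii) rests on PIIINP being tested less often than every 60 and 30 days respectively, which is an assumption.

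This should be corrected before the outcome is programmed. It does not undermine the methotrexate model as a whole. Which population or threshold is clinically right is not judged here.

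**What to change.** 1. Reconcile the two statements of the PIIINP rule to one population, and use it in both Gold and Aurum.
2. Amend Step 2 so that PIIINP results are extracted over at least the 12 months that criterion (ii) already requires.
3. State the look-back for (i) and (iii), and whether (iii) means the most recent result.
4. State how the PIIINP criteria relate to the -15/+45-day window, and which date is the event date when an event rests on them.

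No PIIINP threshold changes. The cost is a few sentences and a longer extraction for one test.

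One tempting addition is to require the latest qualifying result to lie inside the 60-day window. That would be a new restriction and not a correction: at an assumed 91-day spacing, the window would contain a result for only about 60/91 = 66% of randomly timed stops. If the team wants it, it should be a deliberate choice with a stated reason.
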